### Fig. 2. CEM imaging sequence.

2. Additional views will be obtained, when needed (e.g. XCCL (exaggerated craniocaudal lateral) view), to include all breast tissue per clinical protocol.

3. For those women who have not undergone DBT as a part of their screening or diagnostic imaging within 3 month from the study, bilateral DBT study will be performed immediately following the CEM study. A complete bilateral DBT study will be obtained utilizing DBT projections and reconstructed synthetic 2D views. This will include CC, MLO, and LM projections of the affected breast, and CC and MLO projections of the non-affected breast.

[figure not shown]
Patients will be observed for 30 minutes after the contrast injection to ensure the absence of symptoms of delayed reaction to iodine-based contrast as reported by patients. The patient will be encouraged to drink at least 500 ml of water after the procedure.

Imaging quality assurance:

The images will be immediately sent to the radiologist for quality assurance via PACS. Additional images (exaggerated or repeat views) may be obtained for technical issues, if necessary.

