# 3.0 Background\*

3.1 *Current MDACC practice protocols* 

As a major tertiary cancer center, MD Anderson Cancer Center has a significant population of patients who present for staging of known breast

cancer (BC) which was already diagnosed at an outside facility (OSF), or who have OSF imaging findings that are assigned category 5 (highly suspicious with the probability of malignancy >95%) or 4C (suspicious with the probability of malignancy 50-95%) according to the American College of Radiology (ACR) Breast Imaging Reporting and Database System (BI-RADS) on OSF imaging [1]. Precise delineation of the extent of disease in the affected breast and evaluation of the contralateral breast are crucial for surgical treatment planning in BC patients [2]. Even in patients with no known BC, a second opinion at a specialized cancer center can make a significant impact on clinical management, changing the original interpretation in 36-47% of lesions [3, 4]. In patients who present with known BC at MDACC, the rate of upstaging upon second opinion interpretation and possible re-imaging is 25%, which changes surgical management in 12% of patients [5]. At the same time, the reoperation rate after breast conservation surgery in BC patients is 19% [5]. This is suboptimal and may be due to underestimation of tumor size, but this rate is lower than the national rate, which reaches 30% [2].

The current protocol for staging of OSF BC cases consists of a second read of interpretable OSF mammograms or repeating technically suboptimal mammograms, followed by ultrasound, ultrasound-guided and/or stereotactic-guided biopsies, when indicated. Some patients also require breast MRI with second look ultrasound and ultrasound- or MRIguided biopsies, which prolongs work-up and delays treatment.

At our institution, using ultrasound and MRI almost doubles the number of additional suspicious breast lesions found on mammography. 45% of these additional lesions are malignant. The sensitivities of mammography (MG), US, and MRI are 36, 71, and 85%, respectively, and their specificities are respectively 76, 68, and 39%, making MRI the most sensitive, and the MG the most specific modality. 18% of additional malignant lesions at MDA are found on MRI only [6]. Unfortunately, the need for breast MRI often delays treatment due to the limited availability of magnet time. MRI is also an expensive imaging test, further limiting access.

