## 5.3 IMAGING WITH CEM

Safety checklist and IV injection:

The imaging technologist, the study personnel, and the radiologist will be responsible for ensuring the safe administration of IV contrast. IV contrast injections and eligibility screening will be performed in accordance with MDACC institutional policies. Contrast safety will be ensured by following the current UTMDACC DIVISION OF DIAGNOSTIC IMAGING POLICY # 3.30, amendment for CEM (Appendix B).

The imaging technologist and the study nurse or research coordinator will use a patient safety checklist for verifying that the patient has no contraindications for the study.

[figure not shown]
If a patient passes the safety checklist, an IV catheter will be placed in the patient's forearm or antecubital vein in the mammography suite

immediately before the procedure by a trained nurse, mammography technologist, or study coordinator. The patients will be sitting for the injection to minimize vaso-vagal reactions. Low-osmolality iodine-based intravenous contrast (Omnipaque 350 mg I/mL; GE Healthcare or equivalent) will be injected using a power injector, at a rate of 3 mL/s for a total dose of 1.5 mL/kg body weight, but not exceeding 150 ml, followed by a 30 mL saline flush [30-32].

Imaging technique:

CEM will be administered using FDA-approved equipment. The study will be conducted using a full-field digital mammography system capable of providing low- and high-energy exposures to the breast under the same compression, as well as producing subtracted contrast images, such as Senographe Pristina (GE Healthcare, Buc, FR) or an equivalent system.

1. The imaging will start with the affected breast 2 min after contrast injections and will consist of one high and one low energy exposure in succession. The affected breast will be imaged in craniocaudal (CC), mediolateral oblique (MLO), and lateromedial (LM) projections (Fig.1). CC and MLO images will also be obtained of the unaffected breast (Fig. 2).

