## 5.8 Multiple reader study design

Low-energy images produced as a part of CEM are of sufficient quality for clinical interpretation (equivalent to directly acquired 2D mammographic images), and will be interpreted accordingly by radiologists.

The reader study will have 2 components:

1. The first interpretation of the entire CEM study, including all its components, will be done clinically by one radiologist after the exam is performed. Its results will be actionable and will affect the patient's management.

2. Multiple reader study. The results of this study will not be used for clinical care, and will not be reported to the patients or referring clinicians.

Each patient's study will contain LE images (FFDM equivalent), DBT images, and CEM subtraction images. All these components will be separated and presented to radiologists in different combinations for within-subject comparison. As a part of the multi-reader component, the study images for every patient will be reviewed in 4 sets by 5 radiologists each. Images for the same patients will be read by radiologists with an interval of at least 2 month to prevent case memorization.

1. LE (FFDM equivalent) images only

2. LE (FFDM equivalent) with DBT

3. LE followed by DBT followed by CEM subtraction images

4. LE followed by subtraction images (complete CEM study)

The study radiologists will be aware of the patients' inclusion criteria, but will be blinded to the clinical diagnostic reports, any and all comparison images of any modality outside of the assigned protocol, and the pathology report.

5.9 The sequence of the imaging studies and the parameters to be collected are presented below. The reporting will be done using ACR BI-RADS Fifth edition recommendations.

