## 9.0 Inclusion and Exclusion Criteria\*

- 9.1 INCLUSION CRITERIA
  - Female patients 18 years of age or older with known invasive or in-situ BC diagnosed at an outside facility and presenting to MD Anderson for staging with imaging.
  - Female patients 18 years of age or older referred from outside institutions with imaging findings categorized as highly suspicious (BI-RADS 5 or 4C) on outside imaging or on rereview by MD Anderson's radiologists and referred for staging at MDACC.
  - Willingness to participate in the study and ability to provide informed consent.
- 9.2 EXCLUSION CRITERIA
  - •

•

- Breast surgery within 6 months.
- *Known allergy to iodine-containing contrast agents.*
- *History of anaphylactic reaction to any substance that required hospitalization or IV placement.*
- *Renal insufficiency; hyperthyroidism.*
- Detection of non-breast primary or metastatic cancer in the breast.

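### The DBT comparator pools prior DBT up to 3 months old, with no stated coverage requirement, with same-session five-view DBT, and Section 15.3 does not separate the two

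*Combined protocol and SAP*

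**What the plan says.** Section 5.3 (Imaging with CEM) gives every woman the same CEM examination on the centre's equipment. "The affected breast will be imaged in craniocaudal (CC), mediolateral oblique (MLO), and lateromedial (LM) projections", and the other breast is imaged in CC and MLO. The LE images come from the same exposures.

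DBT is handled differently. Item 3 of the same section adds a study DBT only in one group: "For those women who have not undergone DBT as a part of their screening or diagnostic imaging within 3 month from the study". For them, a "bilateral DBT study will be performed immediately following the CEM study", with its content fixed: "This will include CC, MLO, and LM projections of the affected breast, and CC and MLO projections of the non-affected breast". That specification describes the DBT the study acquires. For a DBT already done within the window, the text states no site, set of views, laterality or image quality.

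Section 5.8 nevertheless puts DBT in every reader case: "Each patient's study will contain LE images (FFDM equivalent), DBT images, and CEM subtraction images". Reading set 2 is LE plus DBT, set 3 is LE, DBT and subtraction images, and set 4 is the complete CEM study (LE plus subtraction images).

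Section 2.2 names DBT in all three secondary objectives: accuracy measures for additional lesions, index cancer size, and incremental detection relative to the outside-facility (OSF) diagnosis. Section 15.3 compares outcomes between modalities and has no stratum or sensitivity analysis by DBT source.

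**The concern.** In one group of women, CEM and DBT are taken in the same session, with the same projections of the same breasts. In the other group, CEM is current and complete, while the DBT may be up to 3 months older, may lack a projection or a breast, and may predate the outside biopsy. A pooled CEM-minus-DBT difference therefore carries a modality effect plus whatever date and coverage contribute, and the planned analysis cannot separate them.

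Incremental detection is the clearest case. Section 2.2 measures it against the OSF diagnosis. If a woman's DBT is itself an outside examination, it may be part of the work-up that led to that diagnosis. Any increment credited to that DBT could then come only from re-reading existing images, whereas CEM brings new ones. A result of that kind could be reported as added value of CEM over DBT when part of it reflects which images were available.

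**Working it through.** **Step 1. What each examination must contain, from Section 5.3**

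| | CEM/LE, all women | Study DBT | Prior DBT |
|---|---|---|---|
| Timing | study visit | same session, after CEM | within 3 months |
| Site | study centre | study centre | not stated |
| Affected breast | CC, MLO, LM | CC, MLO, LM | not stated |
| Other breast | CC, MLO | CC, MLO | not stated |
| View count | 3 + 2 = 5 | 3 + 2 = 5 | not stated |

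Only the last column is open.

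**Step 2. Is the prior DBT an outside one?** The documents do not say. Under Section 9.1 participants are women whose cancer was diagnosed, or whose suspicious imaging was done, elsewhere: "Female patients 18 years of age or older with known invasive or in-situ BC diagnosed at an outside facility" is one of the two entry routes. Screening DBT also counts towards the window. Outside DBT is therefore probable for many women, but this is an inference. Section 3.3 gives FFDM plus DBT as standard of care at the study centre, so some prior DBT may be in-house.

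**Step 3. The plan's own figure.** Section 15.2 gives 83 patients and 80% power for CEM versus FFDM accuracy (12-point difference, 20% discordance, two-sided 0.05, mean 1.4 lesions with variance 1, correlations 0.4 and 0.2).

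- Independent pairs: [1.960 × √0.20 + 0.842 × √(0.20 − 0.12²)]² / 0.12² = 106.6.
- Design effect with correlation 0.4 × 0.2 = 0.08: 1 + (1.4 + 1/1.4 − 1) × 0.08 = 1.089.
- Patients: 106.6 × 1.089 / 1.4 = 82.95, so 83.

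The product 0.08 was found by trying variants, because the cited method paper is not in the documents; a correlation of 0.2 gives 94 and 0.4 gives 111. For the present point, what matters is that DBT appears nowhere in the calculation. No power or precision is stated for CEM versus DBT.

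**Step 4. How large could the effect be?** Let f be the share of women contributing a prior DBT, and L the sensitivity lost on it relative to same-session DBT, as read in set 2. Neither is in the documents. If malignant lesions are spread evenly over the two groups, pooled DBT sensitivity shifts by f × L:

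- f = 25%, L = 5 points: 1.25 points
- f = 50%, L = 10 points: 5 points
- f = 75%, L = 20 points: 15 points
- any f, L = 0: 0 points

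These are illustrations under assumed inputs, not estimates. L could also be negative.

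**Step 5. What a same-session analysis would retain.** It keeps 83 × (1 − f) women: about 62 at f = 25%, 41 at 50% and 21 at 75%. Interval width grows by roughly 1/√(1 − f), that is 1.15, 1.41 and 2.00 times.

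**The case against.** Accepting a recent DBT is a sensible, pragmatic choice that spares women a repeat exposure, and CEM versus DBT is only a secondary comparison. Beyond that, a reader might infer that DBT is systematically handicapped by poor outside images. The documents do not support that inference, for five reasons.

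- No site is named for the prior DBT, so calling it outside imaging goes beyond the text.
- Section 5.8 does not have DBT read alone. Set 2 supplies the same current, bilateral, on-site LE images that set 4 uses, including LM of the affected breast. A missing breast or projection on a prior DBT is therefore not left unread; only DBT's increment over LE is at risk. This limits the contralateral and missing-view argument considerably.
- Section 3.1 describes current practice as "a second read of interpretable OSF mammograms or repeating technically suboptimal mammograms". That is a safeguard, so the passage should not be cited only as evidence of poor quality. It is background rather than a study rule for DBT, and it does not cover a technically good DBT of one breast or without LM.
- The direction is not established. Fewer DBT findings could raise specificity, and a DBT taken before biopsy would be free of biopsy change and markers, which could help size measurement.
- Section 16.0 already collects scan dates, so the age of the DBT can be recovered.

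In addition, the workflow figure, the CEM sequence figure and the decision algorithm are not visible in the text available here and may say how prior imaging is handled.

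All of this stands. It removes the claim of a known bias, but not the absence of coverage criteria for a prior DBT or of any analysis by source. The shared LE images also do not resolve the incremental-detection problem, since a prior DBT may still be part of the work-up behind the reference diagnosis.

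**Conclusion.** The point holds in limited form. DBT is a mixed comparator set against a uniform CEM/LE examination, and Section 15.3 pools the two sources, so the secondary CEM-versus-DBT results can be confounded by date and coverage. This matters most for incremental detection against the OSF diagnosis and less for contralateral detection, where the shared LE images help.

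Size and direction cannot be derived from the documents. A reader might take the 5-point shift above as an expected inflation of CEM's advantage; it rests on two assumed inputs, vanishes if prior DBT performs as well, and says nothing about specificity. It also does not follow that the main contralateral and size conclusions must be confined to women with matched DBT. That is a debatable trade of precision and representativeness for comparability.

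The primary CEM-versus-LE comparison and N = 83 are unaffected. This is a cheap improvement, not a flaw that threatens the trial.

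**What to change.** - Record for each woman whether the DBT was same-session or prior, where a prior DBT was done, and which views and breasts it covers. Scan dates need no new field.
- In Section 15.3, pre-specify as a sensitivity analysis that the secondary CEM-versus-DBT comparisons, including incremental detection and index size, are also reported separately for same-session and prior DBT. State any claim of added value over DBT in light of the same-session result.
- Interpret each stratum as a within-woman comparison. Women with and without a prior DBT may differ, so a contrast between strata is not a clean estimate of the effect of DBT source.

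No repeat DBT is requested, and the pooled analysis can stay.

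**Cost:** fields for source and coverage, and one added analysis. The downside is precision: if half the women have a prior DBT (an assumption), about 41 of 83 remain in the same-session subset, with intervals roughly 1.4 times as wide.

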## OTHER IMAGING STUDIES:

Decision making algorithm

### Ultrasound

Due to a subjective nature of ultrasound, the ultrasound images will not be included in the reader study. However ultrasound images and reports will be obtained from the patients' medical records and analyzed to provide correlation per lesion with the FFDM, DBT, and CEM studies.

MRI

When available, MRI reports and MRI images will be obtained from the patients' medical records and analyzed to correlate with the FFDM, DBT, CEM, and ultrasound findings.

Image-guided biopsies

Ultrasound-guided FNA or core biopsies, as well as stereotactic, or MRIguided core biopsies will be performed as a part of routine clinical care, when indicated. The biopsies may also be performed using a CEM-guided biopsy instrument (GE Healthcare Pristina Serena Bright).

The following data will be collected from the biopsy reports:

- Number of core samples
- Needle gauge
- Adequacy of sampling, which for stereotactic biopsies will include the percent of microcalcifications removed, and the number of cores with microcalcifications
- Concordance with the pathology results.

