## 2.2 Secondary Objectives

- To evaluate the sensitivity, specificity, positive and negative predictive value of CEM compared to LE CEM images (FFDM equivalent), DBT and ultrasound for the detection of additional malignant lesions in the ipsilateral and contralateral breast.
- To evaluate the difference of the index cancer size estimation among CEM, LE images, DBT, and ultrasound compared to pathology measurements as the ground truth.
- To evaluate the incremental cancer detection rate provided by CEM, DBT, and US compared to the OSF diagnosis.
- 2.3 Exploratory Objectives
  - To evaluate the rate of referral to breast MRI in the study cohort.
  - To evaluate the performance of MRI for breast cancer diagnosis and compare it with other imaging modalities of CEM, LE images, DBT and ultrasound.
  - To evaluate the feasibility of CEM-guided biopsy of CEMonly detected lesions. The technical success of CEM guided biopsies will be determined by the fraction of biopsies that achieve adequate sampling of the target.

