## 2.4 Hypothesis

We hypothesize that CEM will improve the diagnostic accuracy of incremental breast cancer detection compared to standard 2D mammography and will improve the accuracy of the index cancer size estimation. The overarching goal is to determine whether CEM will reduce the need for breast MRI and decrease the overall time and cost of preoperative imaging evaluation of patients with breast cancer.

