### 3.5 INNOVATION

The use of CEM as a first line modality in the evaluation of breast cancers diagnosed at OSF has not been studied. Our proposed protocol may prove beneficial for improving the time and cost-efficiency of imaging work-up, as well as for the overall optimization of workflow for the benefit of the

*unique population of patients referred from OSF to MD Anderson Cancer Center.* 

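### Where MRI follows an actionable CEM read, the planned MRI–CEM comparison can be selected on the CEM result, and analysing women with both tests as pairs does not remove that

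*Combined protocol and SAP*

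**What the plan says.** The second exploratory objective (Section 2.3, repeated in the Section 1.0 summary) is: "To evaluate the performance of MRI for breast cancer diagnosis and compare it with other imaging modalities of CEM, LE images, DBT and ultrasound". The one before it is: "To evaluate the rate of referral to breast MRI in the study cohort".

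The MRI paragraph of Section 5.3 gives the source of the data: "When available, MRI reports and MRI images will be obtained from the patients' medical records". No MRI is required by the study. Section 3.1 describes current practice in the same way: "Some patients also require breast MRI with second look ultrasound".

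Section 5.8 has one radiologist read the full CEM study clinically: "Its results will be actionable and will affect the patient's management". A separate five-reader study is blinded and does not feed into care. Section 3.5 presents CEM as the starting point of the work-up: "The use of CEM as a first line modality in the evaluation of breast cancers diagnosed at OSF has not been studied". Section 2.4 adds: "The overarching goal is to determine whether CEM will reduce the need for breast MRI". Section 14.2 lists avoiding MRI as a possible benefit.

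Section 15.3 compares outcome measures between modalities with McNemar's test, a weighted generalized score statistic, mixed models or an extended McNemar test. It does not mention MRI or say what happens when a modality is present in only some women. Section 16.0 says that scan and report dates are collected, and the Follow-up paragraph before Section 6.0 says that clinical notes and radiology reports are reviewed.

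**The concern.** A paired analysis protects against differences between women. It does not protect against the way in which women came to be in the paired set. If the CEM result influences who goes on to MRI, CEM's sensitivity and specificity inside the set with both tests differ from those in the cohort. MRI's own figures shift too if the two tests tend to err together.

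The plan itself expects this dependence: it makes the CEM read actionable, hopes that CEM will reduce the need for MRI, and measures referral to MRI as an outcome. MRI availability cannot then be assumed unrelated to the CEM result.

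This is the only head-to-head with MRI in the study, and a reader interested in the overarching goal would look to it. It could show an advantage for either test when the two are equally sensitive, and nothing planned would reveal which way the selection ran.

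**Working it through.** **The plan's own figure.** There is none for the MRI comparison. The only sample size, 83 in Section 15.2, is for CEM versus FFDM. It reproduces: with discordance 0.20 and difference 0.12, lesions = (1.96·√0.20 + 0.842·√(0.20 − 0.12²))² / 0.12² = 106.6. Dividing by 1.4 lesions per woman gives 76.2 women. Multiplying by the design effect 1 + (1.4 − 1)·0.2 = 1.08 gives 82.3, rounded up to 83. It serves below only to gauge precision.

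**Inputs for the illustration**
- MRI sensitivity 85% and specificity 39%: Section 3.1 ("The sensitivities of mammography (MG), US, and MRI are 36, 71, and 85%, respectively").
- CEM sensitivity 85%: assumed equal to MRI, in line with the statement in Section 3.3 that the two are similar.
- CEM specificity 70%: assumed. With the 45% malignant share in Section 3.1, accuracy is 0.45·0.85 + 0.55·0.70 = 76.8%, near the 78.0% and 79.8% quoted in Section 15.2.
- One site per woman, the clinical read scored as the CEM result, and CEM and MRI independent given disease: assumed.
- k, the chance of MRI when CEM was negative at the site divided by the chance when it was positive: assumed. The documents give no value.

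**Sensitivity among women with MRI.** With s = 0.85, CEM sensitivity = s / (s + (1 − s)·k).

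| k | Calculation | CEM sensitivity | CEM minus MRI (true value 0) |
|---|---|---|---|
| 0.5 | 0.85/0.925 | 92% | +7 points |
| 1 | 0.85/1.00 | 85% | 0 |
| 2 | 0.85/1.15 | 74% | −11 points |
| 3 | 0.85/1.30 | 65% | −20 points |

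**Why pairing does not help.** Take 100 women with a cancer site and k = 2, with MRI in 20% of CEM-positives and 40% of CEM-negatives. CEM finds 85, of whom 17 have MRI. It misses 15, of whom 6 have MRI. Among these 23 pairs:
- found by CEM only: 17·0.15 = 2.55
- found by MRI only: 6·0.85 = 5.10
- paired difference: (2.55 − 5.10)/23 = −11 points

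In all 100 women both discordant counts would be 12.75. The imbalance that McNemar's test would assess comes entirely from selection. Weighting each pair by 1 over its referral probability restores 17/0.2 = 85 found and 6/0.4 = 15 missed. That works only if those probabilities are known and above zero.

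**Specificity.** With c = 0.70, CEM specificity among women with MRI = c·k / (c·k + 1 − c). At k = 2 it is 1.4/1.7 = 82%, and at k = 0.5 it is 0.35/0.65 = 54%. Against MRI's 39%, a true +31 points becomes +43 or +15. Selection that makes CEM look less sensitive also makes it look more specific.

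**Correlated errors.** With a CEM–MRI correlation of 0.3 given disease, MRI's apparent sensitivity also moved, between 77% and 89% against a true 85%. The referral patterns ran from 10% of CEM-positives and 40% of CEM-negatives to 50% and 10%.

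**Precision.** If 20%, 30% or 50% of the 83 women had MRI (assumed; 16.6, 24.9 or 41.5 women), power for a 12-point difference under the Section 15.2 assumptions would be about 23%, 33% or 50%.

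**The case against.** **Timing.** A reader might infer that every MRI follows the CEM read. The documents do not say so. Women arrive with outside imaging, and taking MRI when it is available admits examinations done before CEM, which cannot be selected on the CEM result. The content of the workflow figure (Section 5.2) and of the decision algorithm in Section 5.3 is not shown and may hold referral rules. This stands, so the point is confined to MRI that comes after CEM.

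**Data capture.** A reader might also infer that timing is not recorded. Section 16.0 contradicts that: scan and report dates are collected. The reason for referral is not a named item, although the reviewed clinical notes may contain it.

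**Role of MRI in the plan.** The hypothesis proper in Section 2.4 sets CEM against 2D mammography, with index cancer size; MRI enters only in the overarching goal. The MRI endpoint in Section 4.3 is descriptive, and Sections 15.1 to 15.3 never name MRI, so no formal MRI test is clearly planned. This stands, but Section 2.3 does promise a comparison, the wording on modalities in Section 15.3 is broad enough to cover it, and the bias affects estimates as well as tests.

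**Size.** The k values are assumed, and nobody knows at referral that CEM has missed a cancer; any dependence would run through an unclear or discordant work-up. The plan also scores CEM by blinded five-reader consensus and allows up to four additional sites. These points weaken the illustration. The consensus reduces the distortion but does not remove it, because it reads the same images as the clinical read and will correlate with it.

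**Conclusion.** The concern holds for MRI obtained after the CEM read. Inclusion in that part of the comparison can depend on the CEM result, and restricting it to women with both tests does not remove the resulting bias. Neither its direction nor its size can be fixed from the documents. The 92%, 74% and 65% show what modest dependence could do under the stated assumptions; they do not predict what this study will find. If referral is unrelated to the CEM result (k = 1), there is no bias.

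A reader might go further and conclude that the whole MRI comparison is invalid, or that MRI will be falsely favoured by a large margin. The documents support neither: earlier MRI is not selected on CEM, and selection can run either way. The objective is exploratory, and the primary CEM versus low-energy comparison is untouched. The change is worth making because it is cheap and alters what the comparison can be said to show.

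**What to change.** Add a short paragraph on MRI to Section 15.3:

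1. Use the scan and report dates already collected to separate MRI done before the clinical CEM read from MRI done after it, and report the MRI–CEM comparison in each group.
2. Extract the reason for MRI referral from the records already under review. This also helps to identify MRI ordered before the CEM read but performed later, which scan dates alone would place in the second group.
3. Tabulate MRI uptake by clinical CEM result, and CEM accuracy in women with and without MRI, so that any selection is visible.
4. State that the comparison for MRI done after CEM applies only to referred women, and that it does not support a claim that CEM matches, beats or falls short of MRI in the whole cohort.

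A ban on testing is not needed. Weighting by the probability of MRI could be a sensitivity analysis if the numbers allow.

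The cost is one extra field, one table, small cells after the split, and a narrower exploratory claim. Patient care and the sample size do not change.
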